## Sample size

We assume 75% of participants will fall into the mild to moderate group (a) and 25% into the severe group (b). We anticipate that there will be a different effect size in each group so we will test them separately. A reduction in score of 50 is the minimum clinically important difference we aim to achieve. However, we also know that 50% of the control group will improve with NICE suggested treatments

The expected value of the primary outcome for the trial in the control group is 125.4 in the mild to moderate group, and 372 in the severe group. The standard deviation is 53.4 and 66.0 in the mild to moderate group and severe groups respectively. We have assumed that 5% of the control patients will be treated in a more similar way to the intervention group, leading to an inflation of the control group change in outcome measure. This makes a change in the difference between control and intervention of 47.5 that we wish to detect. Using a power of 85%, and alpha of 5% gives 72 in total from the severe group and 48 in the mild to moderate group. Each group is randomised half to intervention and half to control. After allowing for loss to follow-up of 10%, the severe group rises to 80 and the mild to moderate group to 54. Giving a total needed of 134 participants.

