## Stratification

## **Analysis**

Means ± SD values or percentiles appropriate to the distribution will be reported for the primary outcome and secondary outcomes by treatment group. A statistical model will be fitted with IBS severity scoring system[23] as the dependent variable. This will be adjusted for baseline assessment of the IBS severity score. A random effects model will be explored. A point estimate, 95% confidence interval and p-value will be reported for the average treatment effect. Residual values will be examined for an approximate normal distribution. If values are highly skewed then a transformation or robust statistical methods will be used instead.

Mixed linear regression models will be used to compare continuous outcomes between treatment groups by adjusting for corresponding metric calculated at baseline and random site effect.

For assessing group difference in demographic covariates, including age, sex and socioeconomic status, linear regression models will be used to compare continuous and ordinal variables, logistic regression will be used to compare categorical variables, and Poisson regression models will be used to compare event rates, while adjusting for a random site effect. For analysis of adverse events, formal statistical comparisons will only be performed when there are enough observed events. If outliers exist, a robust Poisson regression model will be used instead.

Missing data for secondary outcomes will not be imputed. Available case analysis method will be used for secondary analyses.

Two sided p-value will be reported and a 5% significance level will be used to declare statistical significance. For all above mentioned secondary analyses, the false discovery rate will be controlled using the adaptive Benjamini-Hochberg procedure.

A detailed statistical analysis plan will be drafted and approved by the Trial Management Group before data lock.

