## 14. Adverse events

We are not anticipating Serious Adverse Events as a result of the care pathway as this is a non-CTIMP (Clinical Trial of an Investigational Medicinal Product) study. However, all adverse events defined as those resulting in death, as being life-threatening, requiring hospitalisation or prolongation of hospitalisation, resulting in persistent or significant disability or incapacity to a study participant will be reported in line with sponsor's standard operating procedure for adverse events reporting for non-CTIMP Trials.

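### The robust Poisson model for event rates is triggered by outliers, but the plain model's standard errors fail under any extra variation between patients, with or without an outlier

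*Protocol*

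**What the plan says.** Protocol section 11, Analysis, names this model: "Poisson regression models will be used to compare event rates, while adjusting for a random site effect". For adverse events, "formal statistical comparisons will only be performed when there are enough observed events"; no threshold is given. The next sentence sets the only departure from the plain model: "If outliers exist, a robust Poisson regression model will be used instead".

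The same section sets the level ("Two sided p-value will be reported and a 5% significance level will be used to declare statistical significance") and states, for the secondary analyses, that "the false discovery rate will be controlled using the adaptive Benjamini-Hochberg procedure".

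Section 14 limits what is reported to serious events: "all adverse events defined as those resulting in death, as being life-threatening, requiring hospitalisation or prolongation of hospitalisation", or lasting disability or incapacity. Of these, hospitalisation can plainly recur in one patient during the year of follow-up.

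The protocol mentions no dispersion check, patient-level random effect, negative binomial model or default robust variance.

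**The concern.** A Poisson model fixes each patient's variance at that patient's mean. Here the only extra variation allowed is between sites. If patients at the same site differ in underlying rate, or a few account for several events each, the variance of the counts exceeds the mean and the model's standard error for the log rate ratio is too small.

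The rule looks for a different problem. Outliers are one possible sign of extra variation, but smooth differences between patients produce it with no count that stands out. What counts as an outlier is also hard to say for counts of 0, 1, 2 or 3. The plain model can thus be kept where its standard error is wrong, and the choice depends on the observed data.

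At stake is a chance imbalance in serious events being reported as a harm or benefit of nurse-led care, with an interval that is too narrow.

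**Working it through.** **1. Patients per arm.** Inputs from section 11, Sample size: difference 47.5, SD 66.0 (severe) and 53.4 (mild to moderate), power 85%, two-sided 5%, loss 10%, and "Each group is randomised half to intervention and half to control". A noncentral-t calculation reproduces the protocol: 72 severe (power 85.3%) and 48 mild to moderate (power 85.5%). Then 72/0.9 = 80 and 48/0.9 = 53.3, rounded up to 54, total 134. Evaluable: 72 + 48 = 120, or 60 per arm. The protocol gives no figure for the event-rate analysis beyond the 5% level.

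**2. Large-sample size of the plain test.** Let φ be the variance/mean ratio of per-patient counts. The Poisson standard error is too small by a factor √φ, so the true two-sided size is 2 × [1 − Φ(1.96/√φ)]:

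| φ | 1.96/√φ | True size |
|---|---|---|
| 1 | 1.96 | 5.0% |
| 1.25 | 1.75 | 8.0% |
| 1.5 | 1.60 | 11.0% |
| 2 | 1.39 | 16.6% |

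The size reaches 10% at φ = (1.96/1.645)² = 1.42.

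**3. Simulation at this trial's size.** Assumptions: 60 per arm, equal true rates, Poisson counts (φ = 1) or gamma-Poisson counts (φ > 1), no site effect, Wald test of the log rate ratio with variance 1/events₁ + 1/events₂, and trials with no events in an arm counted as not rejecting. Expected total events are the rate × 120.

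| Events per patient | Expected events | φ = 1 | φ = 1.5 | φ = 2 |
|---|---|---|---|---|
| 0.05 | 6 | 0.4% | 1.8% | 3.3% |
| 0.1 | 12 | 2.7% | 6.5% | 9.8% |
| 0.2 | 24 | 4.5% | 9.7% | 15.0% |
| 0.5 | 60 | 4.8% | 10.8% | 16.0% |

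Repeat runs differ by a few tenths of a point. With very few events the test is conservative, because the counts are too sparse for it to reject. The inflation in step 2 appears as events become more frequent.

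**4. Would an outlier check catch it?** At 0.5 events per patient, the median of the largest count in the trial is 3 under pure Poisson and 4 at φ = 1.5. A maximum of 4 rather than 3 would hardly be called an outlier, yet the false-positive rate is already about 10%.

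**5. Does the site effect help?** This was checked with 10 sites of 12 patients, with fixed site terms standing in for the random effect. At a mean of 1 event per patient, the model-based test rejects 4.7% with no patient-level variation and 17.0% with it (φ about 2 within site). Site terms do not remove the excess.

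**6. Effect of a robust variance.** Without site terms, at φ = 1.5, the sandwich version rejects 5.7% at 0.2 events per patient and 5.8% at 0.5, against 9.7% and 10.8% for the plain test. With ten site terms it rejects 5.9% to 7.7%. The highest value in any setting tried was about 8%.

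**The case against.** The strongest objection is about scope. Section 7 lists no event rate among the primary or secondary end points, and the sentence naming Poisson regression opens with baseline demographic comparisons. Adverse events are the likely application only because the robust-model sentence follows directly on them. Section 14 restricts these to serious events and says none is anticipated from the care pathway, and section 8 excludes many patients at higher risk. At 0.05 events per patient the plain test stays below 5% up to φ = 2. The protocol also does not say whether events or patients with an event are counted; if patients, repeat events cannot inflate the test. All of this stands, and it limits the point.

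Three stronger readings are tempting but unsupported:

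- A reader might infer that the trial's event-rate tests run at two or three times their nominal level. That needs serious events that are both fairly frequent and clustered, and the documents give no figure for either.
- A reader might infer that the requirement for enough events selects the cases where repeat events matter most. Enough events could equally come from many patients with one event each.
- A reader might infer that understated p-values contaminate the false discovery rate procedure. That procedure covers secondary analyses, adverse events are not a listed secondary end point, and whether they belong to that family is unclear.

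It can also be said that the meaning of outlier and of robust Poisson belongs in the SAP, and that section 9 keeps the analysts blind to allocation. Both are fair. But the protocol has already fixed the trigger, so a SAP that follows it inherits the fault, and blinding limits a data-dependent choice of model without making the trigger the right one.

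**Conclusion.** The point holds as a minor one. The rule ties the robust model to the wrong condition: validity of the Poisson standard error depends on variance equalling the mean within site, not on the absence of outliers. At 60 per arm the error is harmless at about 0.05 events per patient for φ up to 2. The false-positive rate is about 10% at 0.1 events per patient with φ = 2, and at 0.2 to 0.5 with φ = 1.5; it reaches 15% to 16% at 0.2 to 0.5 with φ = 2. These figures rest on assumed event rates, assumed dispersion and gamma-Poisson counts.

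The primary analysis, the listed end points and the sample size of 134 are untouched. The case for changing the rule is that it is stated, it is wrong, and replacing it costs almost nothing.

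**What to change.** In section 11, Analysis, delete the outlier condition and state one default: *Event rates will be compared by Poisson regression with robust (sandwich) standard errors in all cases, with site in the model as planned.* Add negative binomial regression as a sensitivity analysis only, so that no choice of primary model remains. Naming the sandwich variance matters, because a robust fit that merely downweights outliers need not correct the standard error.

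Cost: one sentence and no new data or patients. Intervals become somewhat wider when events cluster. When they do not, little changes (4.9% against 4.8% rejection at 0.5 events per patient). A small excess over 5% can remain in samples of this size, up to about 8% in the settings tried.

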## **Subgroup Analyses**

The study is not powered to detect subgroup differences. Interpretation of any subgroup analyses will depend on whether the overall analysis demonstrates a significant treatment group difference. If performed the subgroup analyses will be conducted for the primary outcome and will be interpreted with caution.

## **Analysis Population**

The analyses will follow the intention-to-treat principle. It will include all randomised participants, the data from whom will be analysed in the group to which the subjects were assigned through randomisation regardless of the actual group they ended in. Data will not be truncated due to protocol deviations.

## Within-trial analysis

A separate statistical analysis plan will be drafted and approved by the Trial Management Group before commencement of the within-trial economic evaluation.

#### 12. Process evaluation

In parallel with the clinical trial, A process evaluation of the study in line with MRC guidance[24] will be conducted.

Interviews with patient participants from each arm of the study after completing the intervention or comparison arm will be carried out. We will interview the trial nurses delivering the interventions and a sample of GPs in practices where the intervention is taking place. We will also audio-record intervention consultations to check fidelity.

The aim of these interviews is to explain the trial results and how best to scale the intervention, if it is shown to be effective, through the understanding of:

- 1. how the intervention is delivered to participants and its acceptability to them
- 2. how the intervention is communicated to participants
- 3. how the intervention was delivered by nurses and GPs, any protocol deviations and explanations for this.
- 4. the fidelity of the intervention over time
- 5. how participants respond to the any intervention suggested, how they interact with it, what they do as a result and any unexpected consequences;
- 6. any factors to do with families, friends, participants working environment, the GP practice or wider health service environment that affect intervention implementation during the trial, to try and understand the barriers and facilitators to intervention during the trial and help develop strategies to deal with this if the trial is successful and the approach is to be rolled out more widely.

The process evaluation will be delivered by a trained research assistant using semi-structured interviews either face to face, by Skype or over the telephone and will last for 30-60 minutes. Interviews will be digitally recorded and transcribed verbatim.

Maximum variation of variables across the sample is the goal. Once saturation is reached, i.e. the interviews are not producing new information, they will stop.

Both nurses delivering the intervention will be interviewed on two occasions, after they have seen 10 patients each and then again after they have seen 20 patients. Data collected will include their demographic data (sex, age, ethnicity, and level of education), questions about intervention delivery and fidelity (including any changes made), what went well/could have been improved in the training they received, and the response of the patient to the intervention. Contamination will also be considered, i.e. delivery of any aspects of the intervention to control patients.

Contextual (practice, other) factors will be explored which may act as facilitators or barriers to wider implementation with the intervention nurses and up to 5 GPs participating in the study. Data collected on these GPs will include demographic data (sex, age, ethnicity, highest qualification) including any additional psychological or mental health training in managing people with IBS, number of years working at the practice and if the research site is a training practice.

Up to 15 patients from the intervention arm and 5-10 from the control arm of the study will be interviewed. Patients will be selected for interview to maximise variation in attributes which may be relevant to how the intervention is perceived and how it may affect them, for example their age, gender, marital status, employment status, ethnicity and educational level. We will explore patients' concerns or expectations, understanding of the treatment, responses to the intervention and mechanisms by which outcomes are achieved.

## Consent

For patients, this will be sought at the time of consent for the main trial. Participating GPs will be sent an e-mail or letter inviting them to participate in the interview by the researcher. They will be sent an information sheet and a consent form to either sign and scan back or return in the post prior to the interview. If there is no e-mail response after 2 attempts to contact them, they will not be approached further. Nurses delivering the nurse led arm will be ask to agree to participate in this process evaluation at time of interview and it will be stated in their job plan.

## **Analysis**

Qualitative data from interviews will be analysed using framework analysis[25] based on the MRC recommended constructs[24] supported by NVivo. We will also assess intervention consultation audio-recordings using an intervention checklist.

## 13. Withdrawal

Participants may be withdrawn from the trial either at their own request and are not required to give a reason for this, or at the discretion of the Investigator. Patients who become pregnant, are diagnosed with a new malignancy, undergo abdominal surgery or have significant change in their health during the course of the study will be withdrawn. The participants will be made aware that this will not affect their future care. Participants may withdraw fully from the trial (from the intervention and from further data provision), or from the intervention only but continue to provide data. If the patient withdraws consent; reasons for withdrawal will be sought and recorded, whilst respecting the participants' right to give no reason. Participants will be made aware that should they withdraw the data collected to date will be retained and used in the final analysis.

## 14. Adverse events

We are not anticipating Serious Adverse Events as a result of the care pathway as this is a non-CTIMP (Clinical Trial of an Investigational Medicinal Product) study. However, all adverse events defined as those resulting in death, as being life-threatening, requiring hospitalisation or prolongation of hospitalisation, resulting in persistent or significant disability or incapacity to a study participant will be reported in line with sponsor's standard operating procedure for adverse events reporting for non-CTIMP Trials.

## 15. Regulatory & Ethics Committee Approval

The study shall not commence until the study protocol, information sheets and consent forms have been reviewed and approved from a Research Ethics Committee and relevant NHS/Social Care permission and Regulatory approval is obtained.

The sponsor will be responsible for deciding whether amendments are substantial and non-substantial in collaboration with the Chief Investigator. Where an amendment is required to study documentation that required REC approval, changes will not be implemented until REC approval and HRA categorisation is received. Where an amendment requires local approval this shall be sought prior to the amendment be implemented at each site in accordance with the categorisation given on the HRA approval letter. Should an amendment be required to eliminate an apparent immediate hazard to participants this may be implemented immediately and the REC/HRA and R&D will be notified as soon as possible.

Minor amendments for logistical or administrative purposes may be implemented immediately. Amendments will be logged on the Sponsor's Study Amendment Log and stored in the Trial Master/Site File(s).

Annual Progress Reports shall be submitted to the REC within 30 days of the anniversary date on which the favourable opinion was given – until the end of the study.

A final report shall (where possible) be submitted to the REC within one year after the end of the study.

If the study is terminated prematurely the CI will notify the REC, including the reasons for premature termination.

## 16. Assessment and management of risk

Individual participant medical information obtained as a result of this study are considered confidential and disclosure to third parties is prohibited with the exceptions noted. Medical information may be given to the participant's medical team and all appropriate medical personnel responsible for the participant's welfare.

If information is disclosed during the study that could pose a risk of harm to the participant or others, the researcher will discuss this with the CI and where appropriate report accordingly.

## 17. Peer review

This protocol has been internally reviewed by all members of the research team, members of the East Midlands CRN and lay representatives to assess the ethical aspects of this study and advice on scientific quality of the study. The initial application which is substantially the same as this protocol externally reviewed as part of the process for the award of funding by the NIHR Research for Patients Benefit funding stream.

## 18. Public & patient involvement

Patients have been actively involved in reviewing study documentation (PIS, CRF and study questionnaires). Patient and public representatives are members of the research team, advising on and supporting project progression and will help with preparing a lay summary of the study findings for dissemination.

## 19. Protocol compliance

Accidental protocol deviations may occur at any time. Accidental protocol deviations will be adequately documented on the relevant forms and reported to the Chief Investigator and Sponsor immediately. Deviations from the protocol which are found to frequently recur are not acceptable, these will require immediate action and could potentially be classified as a serious breach

Accidental protocol deviations may occur at any time. Accidental protocol deviations will be adequately documented on the relevant forms and reported to the Chief Investigator and Sponsor immediately. Deviations from the protocol which are found to frequently recur are not acceptable, these will require immediate action and could potentially be classified as a serious breach.

A "serious breach" is a breach which is likely to effect to a significant degree –

- (a) the safety or physical or mental integrity of the subjects of the trial; or
- (b) the scientific value of the trial

In the event of a serious breach, the Sponsor will be notified immediately of any case where the above definition applies during the trial conduct phase

## 20. Data protection and patient confidentiality

All study staff and investigators will comply with the principles of the Data Protection Act 2018 in protecting the rights of study participants with regards to the collection, storage,

processing and disclosure of personal information and will uphold the Act's/Regulations core principles.

Each participant will be assigned a study identity number, for use on all trial documents and the electronic database. Personal data, research data and the linking code will be stored in separate locations. When stored electronically, this will include using encrypted digital files within password protected folders and storage media.

Personal data will be stored for 1 year following the end of the study, so that the Chief Investigator may provide participants with a summary of the research (should they wish to receive a copy). Data generated as a result of this study will be available for inspection on request by the HHTU/Lincolnshire Community Health Services NHS Trust, the REC, local R&D Departments and the regulatory authorities.

## 21. Indemnity

Insurance and indemnity for trial participants and trial staff is covered within the NHS Indemnity Arrangements for clinical negligence claims in the NHS, issued under cover of HSG (96)48. There are no special compensation arrangements, but trial participants may have recourse through the NHS complaints procedures.

